#### **4.4 Subject replacement**

Patients who were prematurely withdrawn from the study for any reason except the occurrence of AEs assessed as possibly or probably related to study treatment could be replaced during the course of the study.

#### **4.5 Blinding**

This is a double-blind study and the allocation of treatments will not be disclosed until clean file has been declared and the database has been locked.

## 5 STATISTICAL AND ANALYTICAL PLANS

### 5.1 Statistical hypotheses

Hypotheses tests will be performed at the 5% alpha level with the aim of proving superiority of NLX-112 compared to placebo on the change from baseline on a number of efficacy parameters. Any inference of superiority of NLX-112 compared to placebo will be based on these tests. Further testing within each treatment (NLX-112 or placebo respectively) at the 5% alpha level will be done with the aim of proving a beneficial shift from baseline, as a result of the IMP intervention.

Considering the small dimension of the study and the many tests performed, statistically significant findings should be viewed more as indicative results rather than confirmatory.

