## 5.8 Multiple comparisons/multiplicity

Statistical tests of efficacy outcomes will be for explorative purposes and no adjustment for multiple tests will be performed.

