### 9.2 Analysis of secondary endpoints

#### 9.2.1 *Statistical inferential analysis of efficacy endpoints*

Absolute change from baseline in efficacy endpoints (secondary and exploratory endpoints) will generally be analysed using a linear mixed model with treatment, visit and the interaction

treatment\*visit as fixed categorical effects and subject within treatment as a random effect. The baseline value of the dependent variable will be included in the model as a continuous covariate, to account for possible differences in change from baseline outcomes due the starting baseline level. Visit will be modelled as a repeated effect. Kenward-Roger's approximation for degrees of freedom will be used.

Providing a significant type III F-test for the interaction effect treatment\*visit, differences between least square estimates of NLX-112 and placebo for the same visit (i.e. from the interaction term treatment\*visit, where visit is the same for both NLX-112 and placebo) will be estimated and the corresponding p-value will be presented in tables. In addition, differences between least square estimates of each post-baseline visit and baseline for NLX -112 and placebo respectively (i.e. from the interaction term treatment\*visit, where treatment is the same for the post-baseline and the baseline visit) will be estimated and the corresponding p-value will be presented in tables.

The model proposed above will be used for FAS and is valid, as long as the underlying data is missing at random (MAR). As a sensitivity analysis, the model will also be run for PPS, serving as a validity check for the main FAS analysis. The sensitivity analysis will be a complete case analysis, i.e., only patients with no missing data for the dependent variable will be used.

Model diagnostics, for example Shapiro-Wilk's test for a normally distributed residual term and Leven's test for the homoscedasticity assumption of the residual term as well as Q-Q plots and plotting residuals vs. predicted values, will be performed. If model assumptions are deemed to be violated, an attempt will be made to transform the dependent variable in order to fulfil model diagnostics.

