A box-cox model will be used to find the most appropriate transformation of data. Lambda values between -3 and 3 will be tested using increments of 0.25. The dependent variable will be transformed accordingly, and the linear mixed model rerun on transformed data. Subsequently, the same model diagnostics as described above will be performed. If model assumptions are deemed to be violated, the linear mixed model approach will not be further pursued for the corresponding dependent variable.

If transforming data according to the above method fails, the analysis will be done using non-parametric methods. A Wilcoxon rank sum test will be used to assess statistically significant differences between active treatment and placebo for relative change from baseline in efficacy endpoints for all post-baseline visits respectively. Furthermore, a Wilcoxon signed rank test will be performed for each post-baseline visit and baseline for NLX -112 and placebo respectively to assess statistically significant differences between each post-baseline visit and baseline for each treatment separately.

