### 10.2.3 Secondary endpoint(s)

#### 10.2.3.1 Unified Dyskinesia Rating Scale (UDysRS) total score

**Table UD 1 UDysRS total score for all Parts (Full analysis set)**

Result category	Assessment timepoint		NLX-112 (N=XX)	Placebo (N=XX)	Total (N=XX)
Measured value	[Assessment timepoint 1]	n	xx	xx	xx
		Mean (SD)	x.xx (x.xx)	x.xx (x.xx)	x.xx (x.xx)
		Median (Min, Max)	x.xx (x.x, x.x)	x.xx (x.x, x.x)	x.xx (x.x, x.x)
	[Assessment timepoint 2]	n	xx	xx	xx
		...	...	...	...
Absolute change from baseline	[Assessment timepoint 2]	n	xx	xx	xx
		Mean (SD)	x.xx (x.xx)	x.xx (x.xx)	x.xx (x.xx)
		Median (Min, Max)	x.xx (x.x, x.x)	x.xx (x.x, x.x)	x.xx (x.x, x.x)
	[Assessment timepoint 3]	LMM a p-value	xxxxx b	xxxxx c	xxxxx d
		n	xxxxx	xxxxx	xxxxx
		...	...	...	...
Relative change from baseline (%)	[Assessment timepoint 2]	n	xx	xx	xx
		Mean (SD)	x.xx (x.xx)	x.xx (x.xx)	x.xx (x.xx)
		Median (Min, Max)	x.xx (x.x, x.x)	x.xx (x.x, x.x)	x.xx (x.x, x.x)
	[Assessment timepoint 3]	n	xxxxx	xxxxx	xxxxx
		...	...	...	...

a) Linear mixed model (LMM) with treatment, visit and the interaction treatment\*visit as fixed categorical effects and subject within treatment as a random effect. The baseline value of the dependent variable has been included in the model as a continuous covariate. Kenward-Roger's approximation for degrees of freedom will be used.

b) p-value for the difference between NLX-112 at the assessment timepoint and at baseline.

c) p-value for the difference between placebo at the assessment timepoint and at baseline.

d) p-value for the difference between NLX-112 and placebo absolute change from baseline at the assessment timepoint.

Data based on the Full analysis set. The session marked as most severe for Part III and IV have been used. For Part III, the highest score for each individual questionnaire item has been used. All UDysRS item scores for Part I, II, III and IV have been summarized pre patient and assessment timepoint and used as input data to the table. N: Number of observations. SD: Standard deviation. NC: Not calculated - number of evaluable observations less than 3. NA: Not available - no evaluable observations. SAS program: [PROGRAM NAME].sas. Run by: [USERNAME] YYYY-MM-DDTHH:MM:SS. Data extracted at: YYYY-MM-DDTHH:MM:SS

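### SAP 5.1 asks within-arm before-after tests to prove an effect of the study drug, which they cannot do, and up to 124 of their p-values per analysis set go into the efficacy tables

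*SAP*

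**What the plan says.** SAP 5.1 sets up two families of tests at the 5% level. The first compares NLX-112 with placebo on change from baseline, and "Any inference of superiority of NLX-112 compared to placebo will be based on these tests". The second tests each arm against its own baseline and "will be done with the aim of proving a beneficial shift from baseline, as a result of the IMP intervention". The section ends with the caution that "statistically significant findings should be viewed more as indicative results rather than confirmatory", and SAP 5.8 adds: "Statistical tests of efficacy outcomes will be for explorative purposes and no adjustment for multiple tests will be performed".

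SAP 9.2.1 carries out both families. The between-arm contrasts are introduced by a condition: "Providing a significant type III F-test for the interaction effect" of treatment by visit. The within-arm contrasts follow in the same paragraph: "In addition, differences between least square estimates of each post-baseline visit and baseline for NLX -112 and placebo respectively" are to be estimated and their p-values tabulated. If the mixed model fails its diagnostics even after transformation, "a Wilcoxon signed rank test will be performed for each post-baseline visit and baseline for NLX -112 and placebo respectively", with no preceding F-test.

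Shells UD 1, CG 1 and KP 1 provide three p-value cells per outcome and visit. Cell b is the "p-value for the difference between NLX-112 at the assessment timepoint and at baseline", cell c is the same for placebo, and cell d is the between-arm comparison. The other efficacy tables are built on UD 1 or KP 1.

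**The concern.** A change from baseline in one arm is the sum of any drug effect, placebo response and time effects. For the diary endpoint it also includes regression to the mean, because inclusion criterion 5 (Protocol 9.4) admits patients on their troublesome-dyskinesia time just before baseline. A test against the arm's own baseline cannot separate these components. Protocol 8.3 makes the same point when it gives the purpose of the placebo control as measuring how endpoints change without active treatment.

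The aim in SAP 5.1 is therefore unattainable by the method attached to it. What is at stake is interpretation: a reader who finds cell b significant and cell c not can take this as evidence for the drug, because the SAP itself assigns that aim to those tests. Unequal arms tilt the pattern. With twice as many patients on NLX-112, the same change in both arms reaches significance more readily there.

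Table CG 1 has a further problem. CGI-C is itself a rating of change and only CGI-S is recorded at baseline, so cells b and c have no baseline value to test against.

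**Working it through.** **1. Number of cells (from the SAP).** Outcomes sent to SAP 9.2.1: UDysRS 5 (UD 1–5), ON time 1, UPDRS 2, CGI-C 1, Kinesia 360 1, KPPS 8 (7 domains and total), PDQ39 9 (8 dimensions and total), HADS 2, ICIQ-OAB 1, ESS 1.

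- Total: 5 + 1 + 2 + 1 + 1 + 8 + 9 + 2 + 1 + 1 = 31 outcomes, in 15 tables.
- Within-arm cells: 31 × 2 visits × 2 arms = 124, of which 1 × 2 × 2 = 4 are CGI-C cells.
- Between-arm cells: 31 × 2 = 62.

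This is per analysis set at Days 28 and 42. Per-protocol copies, and the Visit 9 UPDRS data that shells UP 1 and UP 2 would bring in, are not counted. The count is an upper figure because the F-test may suppress some cells.

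**2. How often the misleading pattern arises (illustration).** The documents give the arm sizes (16 and 8, SAP 4.3) and the two-sided 5% level (SAP 5.7). They give no expected change, SD or visit correlation. I assume identical arms, hence no drug effect, and a common mean change of δ SDs of the change score.

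*Separate one-sample t-tests.* With P(n) the two-sided power from the noncentral t distribution (n − 1 df, noncentrality δ√n), NLX-112 only = P(16) × [1 − P(8)] and placebo only = P(8) × [1 − P(16)].

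| δ | P(16) | P(8) | NLX-112 only | Placebo only |
|---|---|---|---|---|
| 0 | 0.050 | 0.050 | 0.05 × 0.95 = 0.0475 | 0.0475 |
| 0.3 | 0.203 | 0.114 | 0.203 × 0.886 = 0.180 | 0.114 × 0.797 = 0.091 |
| 0.5 | 0.465 | 0.232 | 0.465 × 0.768 = 0.357 | 0.232 × 0.535 = 0.124 |
| 0.75 | 0.801 | 0.449 | 0.801 × 0.551 = 0.441 | 0.449 × 0.199 = 0.089 |

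*Other forms of the test, for δ = 0.3, 0.5 and 0.75.*

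- Pooled variance on 22 df, closer to the mixed model (400,000 simulated trials, visit correlation 0.5 or 0.7 assumed): NLX-112 only about 0.18, 0.34, 0.38; placebo only 0.096, 0.130, 0.087.
- Exact signed rank on normal data (200,000 simulations): NLX-112 only 0.164, 0.346, 0.471; placebo only 0.075, 0.109, 0.091.

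Across methods, NLX-112 only occurs in 16–18%, 34–36% and 38–47% of trials, and placebo only in 7–10%, 11–13% and 9%. At zero common change there is no tilt: about 4–5% each.

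**3. Effect of the F-test.** These results use the pooled-variance model.

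- *The gate also covers the within-arm contrasts.* NLX-112 only falls to 0.011, 0.018–0.019 and 0.020–0.021 when the interaction is tested over the two post-baseline visits (1 df). It is 0.014–0.015, 0.021 and 0.022 if baseline counts as a visit level (2 df).
- *No gate, cell d always printed.* Among the NLX-112-only trials, cell d is non-significant in 89%, 93% and 94%.
- *The gate covers only the between-arm contrast.* The F-test fails, leaving cell d blank, in 94–95% (1 df) or 92–94% (2 df) of the ungated NLX-112-only trials.

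**The case against.** The strongest reply is that the SAP largely disarms the problem itself. The sentence just before the quoted aim confines superiority inference to the between-arm tests, the next paragraph calls significant findings indicative, and SAP 5.8 calls the tests explorative. No planned decision uses cells b or c. This stands, and it is why the point concerns wording and presentation. It does not withdraw the causal aim given to the within-arm tests.

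Second, IMP may simply mean blinded study treatment. The sentence covers both arms, Protocol 10.2 counts placebo as IMP, and SAP 5.5 and 5.9 use the term for all patients; Protocol 9.10, on the other hand, sets IMP apart from placebo. Loose drafting is plausible. Even so, the phrase asserts that an intervention caused a change, with no comparator.

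Third, the size rests on assumed shifts and on one reading of the gate. If the F-test governs the within-arm contrasts, the misleading pattern is rare. If it does not and cell d is printed, the row usually corrects itself. The same holds in the fallback: in a check on normal data using absolute rather than the planned relative change, the rank sum test was non-significant in 90–96% of the NLX-112-only trials. These points stand. The remaining exposure is the reading in which only cell d is gated, because the within-arm p-values then usually appear alone.

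Finally, one could merely relabel the within-arm results as descriptive and keep a confidence interval. A within-arm 95% interval shows whether zero is excluded, so it restates the 5% test being removed.

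**Conclusion.** The concern holds. The aim in SAP 5.1 cannot be met by a one-arm before-after test, and up to 124 p-values per analysis set, twice the number of between-arm ones, are laid out to serve it; four of them, for CGI-C, are undefined. The counts come straight from the documents. The 16–47% range is a risk of misreading under assumed common changes of 0.3 to 0.75 SD with ungated within-arm tests. It is not the error rate of any planned decision, and it drops to about 1–2% if the F-test gates those contrasts. The formal superiority rule is sound on this point. This is a modest correction worth making before the tables are produced.

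**What to change.** - In SAP 5.1, delete the phrase attributing the shift to the IMP intervention, together with the within-arm hypothesis tests. In SAP 9.2.1, delete the within-arm mixed-model contrasts and the signed rank fallback.
- Remove p-value cells b and c from UD 1, CG 1, KP 1 and the tables built on them. Keep the within-arm n, mean (SD) and median already in the shells as description, without a p-value or confidence interval.
- Add one sentence: any statement of drug effect rests only on the between-arm contrast, given as the least-squares mean difference with its 95% CI, or on the rank sum test in the fallback.

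The cost is wording in two SAP sections and 15 shells, plus one CI line per between-arm contrast. Up to 124 p-value cells per analysis set are lost. The 62 between-arm cells stay, and they address the comparison that Protocol 17.6 and 17.7 name for their tests. Data collection does not change. The F-test gate is left as it is, so where it fails a row will carry no inferential result; whether to free the between-arm contrast from it is a separate question.

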### 5.2 Sample size calculation

No formal sample size calculation has been performed. The sample size of 24 patients is considered sufficient to evaluate the primary objective and to allow for a preliminary efficacy evaluation.

### 5.3 Definition of analysis sets

The analysis sets defined for the study are outlined in Table 1.

**Table 1 Analysis sets**

Analysis set	Definition	Use of analysis set
Full analysis set (FAS)	The full analysis set (FAS) will comprise all randomized patients who were dosed.	Safety and efficacy evaluations. See section 10 below for more details.
Per protocol set (PPS)	The per protocol set (PPS) will consist of all patients included in the FAS population who do not have any major protocol violations assessed to compromise the analysis of study data. All protocol violations will be judged as major or minor prior to database lock. The patient must have an overall calculated compliance of 75% to be included in the PPS.	Efficacy evaluations. See section 10 below for more details.

### 5.4 Compliance

Percent compliance will be calculated as:

$$\text{Compliance} = 100 * \frac{\text{number of delivered capsules} - \text{number of returned capsules}}{\text{expected number of used capsules}}$$

Expected number of capsules is derived through the maximum dose tolerated and the steady state dose recorded in the eCRF, the dosing scheduled stipulated in the CSP, actual number of days in each dosing stage (the up-titration period and the stable dosing period) per patient and

comments of dosing stated in the eCRF and the monitoring reports. Data indicating individual treatment compliance will be listed and calculated compliance will be summarized descriptively.

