AEs=adverse events, CGI-C=Clinical Global Impression of Change, ConMeds=Concomitant medications, C-SSRS=Columbia Suicide Severity Rating Scale, ECG=electrocardiogram, ESS=the Epworth Sleepiness Scale, HADS=the Hospital Anxiety Depression Scale, ICIQ-OAB=the International Consultation on Incontinence Questionnaire Overactive Bladder Module, KPPS=the King's Parkinson's disease Pain Scale, MMSE=Mini Mental Status Exam, UPDRS= the Unified Parkinson's Disease Rating Scale, PDQ39=the Parkinson's disease Quality of Life Scale (39-item), UDysRS=the Unified Dyskinesia Rating Scale.

CONFIDENTIAL

Patients will self-administer NLX-112 or placebo 2 times each day, once in the morning and once in the evening. Tablets should be taken with approximately 240 mL water during a meal. Active tablets will contain 0.25 mg NLX-112. Dose escalation will be as follows:

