**Up-titration period (4 weeks):**

- Days 1-4 (0.25 mg/day): 1 tablet in the morning, none in the evening
- Days 5-8 (0.5 mg/day): 1 tablet in the morning and 1 tablet in the evening
- Days 9-12 (0.75 mg/day): 2 tablets in the morning, 1 tablet in the evening
- Days 13-16 (1.0 mg/day): 2 tablets in the morning, 2 tablets in the evening
- Days 17-20 (1.25 mg/day): 3 tablets in the morning, 2 tablets in the evening
- Days 21-24 (1.5 mg/day): 3 tablets in the morning, 3 tablets in the evening
- Days 25-28 (1.75 mg/day): 4 tablets in the morning, 3 tablets in the evening

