## **10.5 Dispensing and accountability**

The IMP received at the site must be inventoried and accounted for throughout the study. The Investigator will maintain a Storage and Accountability Log as well as a Drug Dispensing Log detailing the dates and quantities of study medication received, prepared for and used by each patient and study medication returned or destroyed at the end of the study. Patients must be instructed to return all original containers, whether empty or containing drug.

Unused study drug, and study drug returned by the patient, must be available for verification by the study site monitor during on-site monitoring visits. Any discrepancies between prepared and returned study must be explained and documented. Products deliberately and/or accidentally destroyed by the site or the patient must be accounted for.

Study drug must be dispensed under the supervision of the Investigator or qualified designee, or by a hospital/clinic pharmacist.

At Visits 2, 6 and 7 (Day 1, Day 28, and Day 42) patients will be provided with a small bottle of tablets with explicit dosing instructions, including a dosing instruction sheet as well as a worksheet to keep track of daily doses. The bottle will contain sufficient drug supplies to last until the next scheduled clinic visit. Patients will return the previously used bottle at the next clinic visit including any unused IMP.

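### As worded, SAP 5.4 counts down-titration tablets as used but does not name that stage in the expected count; if its list is complete, the 75% per-protocol cut is met at 60% use of the full 2 mg/day schedule

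*SAP*

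**What the plan says.** SAP 5.4 defines percent compliance as 100 times delivered minus returned units, over the expected number of used units. Neither delivered nor returned is restricted by bottle, visit or period.

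The expected number is built per patient from several inputs: the maximum tolerated and steady state doses in the eCRF, "the dosing scheduled stipulated in the CSP", the "actual number of days in each dosing stage (the up-titration period and the stable dosing period) per patient", and dosing comments in the eCRF and monitoring reports.

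SAP Table 1 then sets the only numeric condition for the PPS: "The patient must have an overall calculated compliance of 75% to be included in the PPS". Patients with major protocol violations are excluded separately.

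On supply, Protocol 10.5 states: "At Visits 2, 6 and 7 (Day 1, Day 28, and Day 42) patients will be provided with a small bottle of tablets". Each bottle is to last until the next clinic visit, and the previous one is returned there. Visit 8 is by telephone, so the Visit 7 bottle covers down-titration (Days 43 to 56) and is reconciled at Visit 9, where the schedule of events (Table 8.1-1) places drug accountability.

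SAP 9.1.1 recognises three periods for adverse event tables: up-titration, stable dosing and down-titration.

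**The concern.** The numerator takes in three periods of tablets, while the stages named for the denominator are two. On that reading the ratio does not equal 100% at full use, and 75% on this scale is not 75% of the tablets due.

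Two outputs depend on it. One is PPS membership: SAP 9.2.1 uses the PPS run as a validity check on the FAS analysis. The other is the compliance row of Table DM 1.

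The last efficacy visit is Day 42. Tablets taken after it say nothing about exposure at the endpoint, yet they can lift a patient over the cut. With about 16 and 8 patients in the two arms, the classification of a single patient can matter to a PPS result.

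**Working it through.** The documents give no compliance figure to reproduce other than the 75% cut, so the check counts tablets from the schedule in Protocol 8.1.

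**Inputs.** Tablet strength: "Active tablets will contain 0.25 mg NLX-112". Up-titration runs in seven four-day steps, from "Days 1-4 (0.25 mg/day): 1 tablet in the morning, none in the evening" to "Days 25-28 (1.75 mg/day): 4 tablets in the morning, 3 tablets in the evening". Stable dosing is 8 tablets a day for 14 days. Down-titration is seven two-day steps from 1.75 mg/day (7 tablets) to 0.25 mg/day (1 tablet). Nominal days are used, and every tablet not returned is taken as used.

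**Tablets due on the full 2 mg/day schedule**
- Up-titration: 4 × (1+2+3+4+5+6+7) = 4 × 28 = 112
- Stable dosing: 14 × 8 = 112
- Down-titration: 2 × (7+6+5+4+3+2+1) = 2 × 28 = 56
- All three periods: 112 + 112 + 56 = 280
- The two named stages: 112 + 112 = 224

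**Score at full use**, if the two named stages are the complete list: 280/224 = 125%.

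**True use at the cut.** 0.75 × 224 = 168 tablets, and 168/280 = 60%.

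**Use up to Day 42 at the cut.** A patient who takes all 56 down-titration tablets needs only 168 − 56 = 112 others, and 112/224 = 50% of the tablets due by Day 42.

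**Lower tolerated doses.** The protocol prints no down-titration table for a patient held below 2 mg/day. Assume the patient stays at the highest dose once it is reached, then steps down from it by 0.25 mg/day every 2 days. For 1 mg/day (4 tablets): up 4 × (1+2+3+4+4+4+4) = 88; stable 14 × 4 = 56; down 2 × (3+2+1) = 12. Full use scores (88+56+12)/(88+56) = 156/144 = 108.3%. The cut is 0.75 × 144 = 108 tablets, and 108/156 = 69.2%. Other doses follow in the same way:

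| Highest dose (mg/day) | Up | Stable | Named stages | Down | All | Score at full use | True use at the 75% cut |
|---|---|---|---|---|---|---|---|
| 2.0 | 112 | 112 | 224 | 56 | 280 | 125.0% | 60.0% |
| 1.75 | 112 | 98 | 210 | 42 | 252 | 120.0% | 62.5% |
| 1.5 | 108 | 84 | 192 | 30 | 222 | 115.6% | 64.9% |
| 1.0 | 88 | 56 | 144 | 12 | 156 | 108.3% | 69.2% |
| 0.5 | 52 | 28 | 80 | 2 | 82 | 102.5% | 73.2% |

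**After correction at 2 mg/day.** With down-titration added to the denominator, full use scores 280/280 = 100% and the cut needs 0.75 × 280 = 210 tablets. With counts limited to the Visit 2 and Visit 6 bottles, full use scores 224/224 = 100% and the cut needs 168 of the 224 tablets due by Day 42.

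**The case against.** The strongest reply is that the bracket qualifies only the count of actual days. Up-titration and stable dosing vary in length with visit windows and tolerability. Down-titration is fixed at two days a step, so it can be derived from the steady state dose and the protocol schedule, which SAP 5.4 lists as a separate input. The word *overall* in Table 1 fits that reading, and full use would then score 100%. This is possible but strained. The bracket reads as a definition of the dosing stages, and SAP 9.1.1 shows that the authors had three periods in view. Nothing in 5.4 says that down-titration is added, or that the numerator stops at Day 42. Two programmers could score the same patient 100% or 125%.

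Three stronger inferences are tempting, and the documents do not support them.

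- *A patient who takes none of the stable-phase tablets would enter the PPS.* Such a patient could reach (112 + 56)/224 = 75%, but the numeric cut is necessary, not sufficient. Major violations are judged before database lock, and Protocol 9.8.1 says interruptions of 3 days or more may lead to discontinuation. The review may well exclude that patient.
- *Over-use would go unnoticed.* The 75% rule has no upper limit, but Protocol 11.2.1.17 sends overdoses to the deviations log, Protocol 10.5 requires accountability discrepancies to be explained, and individual compliance is listed.
- *Table 1 asks for exactly 75%.* The missing words *at least* are an editorial slip; the intent is plain.

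It is also fair that the stakes are modest. The PPS run is a sensitivity analysis, SAP 5.1 treats significant findings as indicative, and PPS tables are produced only if the two sets differ.

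**Conclusion.** The point holds as a mismatch in the wording of SAP 5.4. If the two named stages are the complete list, full use of the 2 mg/day schedule scores 125% and the 75% cut corresponds to 60% of all tablets, or to as little as 50% of those due by Day 42 when every down-titration tablet is taken.

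The 125% and 60% figures should not be read as applying to every patient. They belong to the full 2 mg/day schedule on nominal days. At lower doses, under the step-down assumption above, the inflation falls to 108.3% at 1 mg/day and 102.5% at 0.5 mg/day. The meaning of the single cut therefore shifts with tolerated dose.

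The effect stops at PPS membership and the compliance summary in Table DM 1. FAS efficacy and safety results are unaffected. The documents give no basis for estimating how many patients would change set.

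**What to change.** Make the numerator and denominator of SAP 5.4 cover the same period, in one of two ways:

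1. Add the down-titration days to the expected count. This keeps *overall* in Table 1 accurate.
2. Limit delivered and returned counts to the bottles dispensed at Visits 2 and 6. This measures exposure up to the last efficacy visit, which suits the purpose of the PPS, but *overall* in Table 1 would then need rewording to say compliance up to Visit 7.

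Either gives 100% at full use. State in 5.4 how the expected count is formed for a patient held below 2 mg/day.

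Editorial tidying at the same time: write *at least 75%* in Table 1, and replace capsules with tablets in the formula. The SAP formula also differs from the one in Protocol 17.4.3 (one minus returned over delivered), and SAP Table 2 does not list that change; a line there would complete the record.

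The cost is about one sentence in 5.4, a few words in Table 1 and a matching change in the compliance program, to be settled before database lock. No extra data are needed.
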